The appearance of a retroverted acetabulum is primarily verified on the anterior-posterior (AP) radiograph by the cross-over sign (COS; anterior acetabular rim crosses the posterior rim) and the posterior-wall sign (PWS; posterior acetabular rim is medial to the center of the femoral head) (1). The prevalence of radiographic signs of acetabular retroversion, on the combined presence of COS and PWS, is 5-7% among the general population (8-10). Currently, the standard treatment for symptomatic acetabular retroversion is an anteverting periacetabular osteotomy (PAO) to prevent FAIS (11). PAO is associated with risks of complications and a subsequently long period of rehabilitation.

The hip joints are directly affected by the position of the pelvis. The pelvis is balanced on the femoral heads via the acetabular sockets, carrying the load of the upper body (12, 13). Anterior pelvic tilt is an anteversion of the pelvis around a bicoxo-femoral axis in the sagittal plane and is positively correlated with lumbar lordosis in standing (13-17). A higher degree of anterior pelvic tilt functionally increases superior femoral head cover (1, 18), and thereby increases the risk of FAIS (19). Especially in standing, sitting, and squatting positions, the level of anterior tilt has been found to correlate with FAIS (20). Thus, excessive anterior pelvic tilt may cause or enhance FAIS in patients with acetabular retroversion. A systematic review and meta-analysis (21), on various causes of FAIS, concluded that physical therapy has positive short-term results on self-reported pain and function. Recent studies on exercise interventions for various types of FAIS patients included exercises aiming at improving general core stability, pelvic control, and advice on posture (22-28). However, there is currently no evidence on non-surgical treatment of reducing excessive anterior pelvic tilt, including patients with acetabular retroversion (29).

To our knowledge, this is the first study investigating a targeted exercise intervention aiming at reducing symptoms and anterior pelvic tilt in patients with acetabular retroversion. Feasibility will be assessed as it may be of importance to the outcome of a progressive home-based exercise intervention in patients with symptomatic acetabular retroversion.

Objective

To investigate feasibility of an 8-week progressive home-based exercise intervention and change in patient-reported symptoms and pelvic tilt, in a prospective cohort of patients with radiographic verified acetabular retroversion, and excessive anterior pelvic tilt.

Primary hypothesis:

In a paired design, the improvement in '*The Copenhagen Hip and Groin Outcome Score*' pain-subscale (HAGOS questionnaire), following an 8-week exercise intervention, will be larger in comparison with the prior control period.

Secondary hypotheses:

- The exercise intervention is feasible in terms of adherence to exercise, exercise-related pain, drop-outs, and adverse events.
- The improvements in the remaining HAGOS subscale scores on symptoms, level of function, and quality of life, following an 8-week exercise intervention, will be larger in comparison with the control period.
- The improvements in the EQ-5D-3L questionnaire, following an 8-week exercise intervention, will be larger in comparison with the control period.
- The reduction in the degree of anterior pelvic tilt evaluated by EOS imaging, following an 8-week exercise intervention, will be larger in comparison with a control period.

STUDY METHODS

Design

The study was designed as a single-center, non-consecutive, unblinded prospective cohort study using patients as their own controls. The change between an 8-week control period prior to the intervention and the following 8-week exercise period will be reported.

Exercise intervention

A physiotherapist (the project manager) informed the patients about the relation between the hip condition and the purpose of the exercise program, provided advice on activity and sports modification, and instructed in exercises. The exercise program was an 8-week progressive home-based exercise intervention with optional, supervised booster-sessions and opportunity to contact the project manager by mail or phone in case of questions regarding the exercise program. After the 8-week exercise period was completed, the patients were encouraged to continue with the exercise program for another 16 weeks.

The exercise program was standardized and non-supervised consisting of four general elements: stretching for posterior pelvic tilt mobility, strengthening hip abductors and extensors, improving body core stability, and movement control for actively tilting and/or keeping the pelvis posteriorly.

Statistical Analysis plan

Each exercise session began with stretching exercises, followed by muscle strength training and ended with specific posture improving exercises on tilting the pelvis posteriorly.

The exercise program was intended to be completed three to four times a week, with a rest day in between. In the first two weeks (module I), the duration of the exercise program was approximately 30 minutes to complete. For the remaining six weeks (module II), the exercise program gradually took longer time to complete (i.e. 45 min.), as the number of repetitions increased.

In case of any adverse events, or other challenges related to the exercise program, the project manager was contacted, and a booster-session was arranged. In cases of drop-outs, the referring physician decided whether the patient should be seen in the outpatient clinic again.

Experienced hip-related pain exceeding 4 on a 0-10 scale, where 0 = *no pain* and 10 = *worst possible pain*, was considered as alarming pain and the exercises was subsequently adjusted. The level of pain before, during, and after exercise were noted in the training diary along with the use of over-the-counter analgesics.

Overview of the progression of exercises

Module I – Exercises (first two weeks)	Week 1-2
#1 Stretching the anterior hip	2 sets of 30 sec.
#2 Stretching the low back	2 sets of 30 sec.
#3 Stretching the anterior thigh	2 sets of 30 sec.
#4 Strengthening the hip abductors	2 sets of 10 reps.
#5 Strengthening the hip external rotators (Clamshell)	2 sets of 10 reps.
#6 Spinal mobility (Cat & Camel)	1 set of 10 reps.
#7 Core stability (Bird Dog)	3 sets of 10 reps.
#8 Movement control in lying (Pelvic tilt)	2 sets of 10 reps.
#9 Core stability (Static plank)	2 sets of 15 sec.
#10 Strengthening the abdominal muscles (Crunch)	2 sets of 10 reps.
#11 Strengthening the abdominal muscles (Oblique crunch)	2 sets of 10 reps.
#12 Movement control in standing (Supported pelvic tilt)	1 set of 10 reps.
#13 Movement control in standing (Unsupported pelvic tilt)	1 set of 10 reps.

Module II – Exercises (from week 3 to 8)	Week 3-4	Week 5-6	Week 7-8
#1 Stretching the anterior hip	2 sets of 30 sec.	2 sets of 30 sec.	2 sets of 30 sec.
#2 Stretching the low back	2 sets of 30 sec.	2 sets of 30 sec.	2 sets of 30 sec.
#3 Stretching the anterior thigh	2 sets of 30 sec.	2 sets of 30 sec.	2 sets of 30 sec.
#4 Strengthening the hip abductors	2 sets of 10 reps.	3 sets of 10 reps.	4 sets of 10 reps.
#5 Strengthening the hip external rotators (Clamshell)	2 sets of 10 reps.	3 sets of 10 reps.	4 sets of 10 reps.
#6 Spinal mobility (Cat & Camel)	1 set of 10 reps.	1 set of 10 reps.	1 set of 10 reps.
#7 Movement control in lying (Dying bug)	2 sets of 10 reps.	3 sets of 10 reps.	4 sets of 10 reps.
#8 Movement control in lying (Single leg pelvic tilt)	2 sets of 10 reps.	3 sets of 10 reps.	4 sets of 10 reps.
#9 Strengthening the hip extensors	2 sets of 10 reps.	3 sets of 10 reps.	4 sets of 10 reps.
#10 Core stability (Dynamic plank)	2 sets of 10 reps.	3 sets of 10 reps.	4 sets of 10 reps.
#11 Movement control in standing (Sup. pelvic tilt)	1 set of 10 reps.	1 set of 10 reps.	1 set of 10 reps.
#12 Movement control in standing (Unsup. pelvic tilt)	1 set of 10 reps.	1 set of 10 reps.	1 set of 10 reps.

Abbreviations: Sec.=Seconds, Reps. Repetitions, Sup.=Supported, Unsup.=Unsupported

Selection of subsample for physical performance assessment

A subsample (20 patients) of the included patients was randomly selected to be investigated for isometric muscle strength, kinematic and kinetic outcomes during gait and functional tasks in a 3-dimensional motion laboratory. The explorative outcomes will be reported in secondary analyses not specified in the current SAP.

Sample size

The sample size calculation was based upon paired means calculation. The minimal clinical important difference (MCID) for the HAGOS pain-subscale was estimated being 10 % (half a standard deviation) (30). A minimum of 36 patients was required (10 % pre-posttest difference on HAGOS pain-subscale, SD=20.6 (30), alpha = 0.05, power = 80 %). An additional of four patients were added due to the risk of dropout.

Stopping guidance

There was no overall stopping guidance in the study or interim analysis of adverse effects. However, the training was stopped, and the referring physician contacted if individual patients experienced pain above 4 on a 0-10 Numeric Ranking Scale related to the training program, that could not be reduced by adjusting the exercises during a booster-session.

Timing of analysis

The primary endpoint was after the 8-week exercise period.

There were four time points at which the outcomes were measured, framing three consecutive periods: control period, exercise period, and an additional 16-weeks exercise period. Analysis of data from the 16 weeks of additional exercise is not a part of this SAP.

Timing of outcome assessments

Time points at which the outcomes were measured are presented in Table 1. Outcomes are defined in the *Analysis* section.

Table 1 – Timing of outcome assessments

Outcomes	Control period	Baseline	Primary endpoint
		Minus 8-weeks before exercise intervention	Start-up of exercise intervention
Primary outcome			
PROM: HAGOS pain subscale	x	x	x
Secondary outcomes			
PROM: HAGOS remaining five subscales	x	x	x
EQ-5D-3L	x	x	x
EOS scanning: Pelvic tilt	x	x	x
Explorative outcomes			
PROM: Global Perceived Effect			x
Oxford Hip Score	x	x	x

Abbreviation: PROM (Patient-Reported Outcome Measure)

STATISTICAL PRINCIPLES

Descriptive data and fitted regression residuals from the mixed-effects linear regression model will be visually assessed for Gaussian distribution by use of QQ-plots and frequency histograms, and statistically tested using the Shapiro-Wilk test. Parametric and/or non-parametric statistical analyses will be used appropriately. A two-tailed P-value of $P \leq 0.05$ will be considered statistically significant, and estimates will be presented with 95% confidence intervals. A primary analysis following the Intention-To-Treat (ITT) principle and a secondary Per Protocol (PP) sensitivity analysis will be conducted (elaborated later in the *Analysis* section).

Adherence

Adherence to the exercise program (frequency) was recorded in a self-reported training diary. Adherence was defined as at least 75% completion of the prescribed exercise program in the 8-week period. The patients were instructed to exercise 3-4 times a week (i.e. 24-32 times over eight weeks) accordingly. Thus, at least 18 exercise sessions (75% of 24 exercise sessions), must have been completed to achieve acceptable compliance.

Exercise-related pain and adverse events

Exercise-related pain was recorded in a self-reported training diary, from 0-10 on a Numeric Ranking Scale (NRS) before, during and after exercising. A level of hip-related pain equal to and above 5 was defined as alarming values and subsequently adjustments were done as described above. Potential adverse events were noted in the training diary or reported by phone and email to the project manager. The use of hip-related analgesics and general comments on the exercise program were noted in the diary.

Protocol deviations

The following minor adjustments/additions were made after trial registration on Clinicaltrials.gov and inclusion of the first patient.

- The assessment of feasibility was added to the study objective because of the novelty and potential importance of the exercise program.
- The secondary outcome '*Radiographic measurement of pelvic tilt in the frontal plane, defined as the distance (in mm.) between the sacro-coccygeal joint and the symphysis*' was changed to the '*Radiographic measurement of pelvic tilt in the sagittal plane, defined as the angle (in degrees) between a horizontal line and a line connecting the upper border of the symphysis with the sacral promontory*'. From inspecting our radiographic data, we learned that pelvic tilt measured in the sagittal plane were more reliable compared to frontal plane images. Moreover, the adjustment resulted in that no images had to be excluded due to poor image quality.
- Due to two dropouts early in the study, two additional patients were recruited. However, since only one patient subsequently dropped out, a total of 39 patients completed the training out of 42 included patients.
- Three patients did not get the last EOS-scanning done after the end of the exercise period due to pregnancy (n=2) and a defect apparatus (n=1).

TRIAL POPULATION

Patients between 18 to 40 years old were included from Odense University Hospital outpatient clinic (Denmark), with verified acetabular retroversion (positive COS and PWS) from a frontal pelvic radiograph in standard standing position, not eligible for periacetabular osteotomy and able to take part in the intervention. Patients were excluded if they had a pelvic-tilt-ratio greater than 0.5 (31) (the height of the obturator foramen divided by the height of the lesser pelvis) indicating posterior pelvic tilt, radiographic sign of hip osteoarthritis (< 2 mm. joint space), previous lumbar, pelvic or hip related surgery, conditions not allowing exercise therapy, a body mass index (BMI) above 35 and not understanding spoken and/or written Danish language.

Flowchart of patients' progress through the study is presented in Figure 1.

Statistical Analysis plan

[figure not shown]

Figure 1 – Flowchart of patients' progress through the study

Patient characteristics are presented in Table 2.

Table 2 – Patient characteristics at the beginning of the control period (n=42)

Patient characteristics	
Sex, male/female, n (%)	
Age, years	
BMI, kg/m ²	
Height, m	
Weight, kg	
Affected hip	
Bilateral, n (%)	
Left, n (%)	
Right, n (%)	
Patient-reported outcome measures	
HAGOS, score from 0 to 100	
Pain	
Symptoms	
Physical function in daily living	
Physical function in Sport and Recreation,	
Participation in Physical Activities	
Hip and/or groin-related Quality of Life	
EQ-5D-3L, index score	
Pelvic tilt	
Pelvic tilt, degrees	
Abbreviations: BMI (body mass index), FAIS (femoroacetabular impingement syndrome), n (numbers)	
* Gaussian distributed data will be presented as standard deviation (SD), otherwise as median and interquartile range (IQR)	

ANALYSIS

Primary outcome definitions

Between-period change in condition-specific questionnaire The Copenhagen Hip and Groin Outcome Score (HAGOS) *pain* subscale on a 0-100 scale, with zero representing extreme hip and/or groin problems and 100 representing no hip and/or groin problems (30). HAGOS has shown good evidence of reliability, validity and responsiveness in young to middle-aged patients with longstanding hip and/or groin pain (55, 56).

Secondary outcome definitions

1. Between-period change in the remaining five HAGOS-subscales (30) (*Symptoms, Physical function in daily living, Physical function in Sport and Recreation, Participation in Physical Activities and hip and/or groin-related Quality of Life*).
2. Between-period change, in the generic questionnaire European Quality of Life - 5 Dimensions (EQ-5D-3-Levels) questionnaire (32), (index value set for Denmark). The upper EQ-5D index value = 1 indicates full health (indicated by “no problem” in all domains), whereas EQ-5D index value = 0 represents death. In addition, the overall health state the actual day is marked on a numeric scale on which the best state is marked 100, and the worst state is marked 0. Psychometric properties for EQ-5D-3L in patients having FAIS is not reported, but EQ-5D-3L is validated as a generic measure of general health (33).
3. Between-period change in pelvic tilt (in degrees) was measured with EOS scanning in standing position in the sagittal plane as the angle between a horizontal line and a line connecting the upper border of the symphysis with the sacral promontory (34). EOS® imaging system is a low-radiation roentgen scanner capturing the selected body part of a person in a standardized standing position with the option to acquire orthogonal views simultaneously in the frontal- and sagittal plane (35). EOS provides diagnostic qualities similar to conventional X-ray using 44 % less radiation when radiographic signs of acetabular retroversion are assessed (36). EOS® imaging system has shown excellent reliability in measuring the sagittal alignment of the pelvis (37). In comparison with radiographs, EOS® is found valid (38) and reliable (39) in assessing pelvic configurations.

Data quality

All patient-reported outcomes will be entered twice to check for entry errors. Fifty randomly selected sagittal EOS scans across the three time points will be assessed for inter-observer reliability regarding pelvic tilt.

Analysis methods

Repeated measurements from a particular patient are likely to be more similar to each other than measurements from different patients, and this correlation needs to be considered in the analysis of the resulting data (40). Longitudinal measurements are not independent of one another, due to the individual baseline value, and time factor, which must be taken into account (40).

A mixed-effects linear regression model will be used accordingly to the longitudinal design and will accommodate missing data in the analysis under the assumption “missing at random,” thus, the analyses will follow the *Intention To Treat* (ITT) principle (40).

Primary analysis:

Under the assumption of normal distributed residuals, a mixed-effects linear regression model will be used to investigate the between-period change on the dependent continuous outcome variable (HAGOS subscale pain). A dummy-coded variable, indicating the three time points at which the measurement was taken, is framing the control period and the intervention period.

Sensitivity analysis:

A ‘*Per-Protocol analysis*’ for patients demonstrating the a-priori-defined acceptable adherence to exercise ($\geq 75\%$) will be performed.

Secondary analysis:

Change between-period comparisons in the remaining five HAGOS subscales, EQ-5D-3L, and pelvic tilt will be tested using a mixed-effects linear regression model as described in the primary analysis.

Post hoc analysis:

A responder/non-responder analyses will be carried out by investigating the exercise period change on the HAGOS pain subscale (Y-axis) against HAGOS pain subscale baseline score, pelvic tilt, age and BMI (X-axis), respectively. The *Minimal Clinical Important Difference* (MCID) of 10 % in the HAGOS pain subscale (30) will be marked as a horizontal lines ($Y=\pm 10$). Patients with change scores equal to and larger than the MCID will be defined as responders to the exercise intervention.

Statistical Analysis plan

Table 3 – Outcome change scores

	Control period change Mean, [95% CI], P-value	Exercise period change Mean, [95% CI], P-value	Between periods change Mean, [95% CI], P-value
Primary outcome			
HAGOS pain			
ITT			
PP			
Secondary outcomes			
HAGOS symptoms			
ITT			
PP			
HAGOS ADL			
ITT			
PP			
HAGOS Sp/Re			
ITT			
PP			
HAGOS Ph/Ac			
ITT			
PP			
HAGOS QoL			
ITT			
PP			
EQ-5D-3-L			
ITT			
PP			
Pelvic tilt			
ITT			
PP			

Abbreviations: ITT=Intention To Treat (Mixed-effects linear regression model), PP=Per Protocol, ADL= *Physical function in daily living*, Sp/Re= *Physical function in Sport and Recreation*, Ph/Ac= *Participation in Physical Activities*, QoL= *hip and/or groin-related Quality of Life*

Clinical perspective

This study will provide information regarding feasibility and responder characteristics of a standardized progressive home-based training intervention for patients with symptomatic acetabular retroversion and excessive pelvic tilt.

REFERENCES

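### The 36 patients and 80% power belong to one pre-post change in HAGOS pain, not to the primary between-period comparison, for which the SAP gives no SD, correlation or power

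*SAP*

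**What the plan says.** The Sample size section says: "The sample size calculation was based upon paired means calculation". The minimal important difference for HAGOS pain "was estimated being 10 % (half a standard deviation) (30"). Then: "A minimum of 36 patients was required (10 % pre-posttest difference on HAGOS pain-subscale, SD=20.6 (30), alpha = 0.05, power = 80"%. Four patients were added for dropout.

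The primary target is stated elsewhere, consistently, as something else:

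- **Primary hypothesis:** the improvement "following an 8-week exercise intervention, will be larger in comparison with the prior control period".
- **Design:** "The change between an 8-week control period prior to the intervention and the following 8-week exercise period will be reported".
- **Primary outcome definitions:** "Between-period change in condition-specific questionnaire The Copenhagen Hip and Groin Outcome Score (HAGOS"), pain subscale.
- **Primary analysis:** "a mixed-effects linear regression model will be used to investigate the between-period change on the dependent continuous outcome variable", with a dummy-coded variable for three time points.
- **Table 3:** separate columns for the control-period change, the exercise-period change and "Between periods change Mean, [95% CI], P-value".

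Under Protocol deviations, 42 patients were included and 39 completed the training.

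**The concern.** Write Y1, Y2 and Y3 for HAGOS pain at the start of the control period, at baseline and at the end of exercise. The sample size is for one difference between two of these. The primary comparison is (Y3 - Y2) - (Y2 - Y1) = Y3 - 2·Y2 + Y1. It uses three measurements, counts the middle one twice, and generally has a larger variance than a single change. Table 3 lists the two quantities in different columns, so the SAP itself treats them as distinct.

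The SAP's only power figure will naturally be read as the power of its primary test. A non-significant between-period result would then be judged against 80% power that was never shown for that comparison.

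A second ambiguity adds to this. Calling 10 points half an SD (20.6/2 = 10.3) suggests that 20.6 is the SD of a score, while the calculation uses it as the SD of a change.

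**Working it through.** **Inputs from the SAP:** difference 10 points, SD 20.6, two-sided alpha 0.05, 36 patients required, 42 included, 39 completed.

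**Assumptions, none given by the SAP:** a true contrast of 10 points (no mean change in the control period); equal SDs of the two changes unless stated; all correlations; for the mixed model, a known covariance, 38 to 80 degrees of freedom, and 42, 42 and 39 HAGOS scores at the three visits.

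**1. The SAP's own figure.** Paired t-test, noncentrality (10/20.6)·√n. Power is 0.797 at n = 35 and 0.808 at n = 36. The stated 36 reproduces exactly for one change with 20.6 as the SD of that change.

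**2. What 20.6 measures.** With equal score SDs σ and 8-week correlation ρ, the SD of a change is σ·√(2(1-ρ)). This equals σ only at ρ = 0.5. If 20.6 is a score SD, ρ = 0.75 gives a change SD of 14.57 and n = 19, and ρ = 0.8 gives 13.03 and n = 16. So the two uses of 20.6 agree, and 36 reproduces, only at ρ = 0.5.

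**3. Correlation r between the two changes.** Y2 enters them with opposite signs. With equal score variances, r = (2ρ - ρ13 - 1)/(2(1-ρ)), where ρ13 is the 16-week correlation. Equal correlations (ρ13 = ρ) give r = -0.5. Decaying correlations (ρ13 = ρ²) give r = -(1-ρ)/2, for example -0.25 at ρ = 0.5.

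**4. Reading A: 20.6 is the SD of one change.** With equal SDs, the contrast SD is 20.6·√(2(1-r)). With control-change SD c it is √(20.6² + c² - 2·r·20.6·c).

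| Control-change SD | r | Contrast SD | Power, n = 36 | Power, n = 39 |
|---|---|---|---|---|
| 20.6 | -0.5 | 35.68 | 0.373 | 0.400 |
| 20.6 | -0.25 | 32.57 | 0.433 | 0.464 |
| 20.6 | 0 | 29.13 | 0.517 | 0.551 |
| 10 | -0.5 | 27.03 | 0.579 | 0.615 |
| 10 | 0 | 22.90 | 0.722 | 0.757 |
| 5 | -0.5 | 23.50 | 0.699 | 0.736 |
| 5 | 0 | 21.20 | 0.786 | 0.819 |

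For 80% power the contrast SD may be at most 20.82 at n = 36, or 21.72 at n = 39.

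Mixed model under reading A:

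- Equal SDs: 42-43% for equal correlation and 48-56% for decaying correlation (0.5 to 0.9).
- Control-change SD 10: 64-79%. Control-change SD 5: 75-84%. Both take score SDs of 15 to 25 at the first two visits.

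**5. Reading B: 20.6 is the SD of a score, mixed model.** SE is that of Y3 - 2·Y2 + Y1 by generalised least squares.

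| 8-week ρ | SE, equal | Power, equal | SE, decaying | Power, decaying |
|---|---|---|---|---|
| 0.5 | 5.55 | 42-43% | 5.08 | 48-49% |
| 0.6 | 4.97 | 50-51% | 4.46 | 59-60% |
| 0.7 | 4.30 | 62-63% | 3.79 | 73-74% |
| 0.75 | 3.93 | 70-71% | 3.42 | 81-82% |
| 0.8 | 3.51 | 79-80% | 3.03 | about 90% |

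Power reaches 80% at ρ of about 0.80 (equal) or 0.74 (decaying), and rises further above that: at ρ = 0.9 with equal correlation it is about 97-98%.

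**6. Precision.** The expected 95% CI half-width for a single change at n = 39 is 6.7 points. For the contrast under the mixed model it is 9.3-11.2 points under reading A with equal SDs. Under reading B it runs from 11.0-11.2 (equal 0.5) down to 6.0-6.1 (decaying 0.8).

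**7. Control-period drift.** If the control period changes by +2 or -2 points beside a 10-point exercise change, the contrast is 8 or 12. Reading A with equal SDs at n = 36 then gives 26-36% or 50-67%.

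**The case against.** - **The pair could be the two periods.** The primary hypothesis speaks of a paired design, so 20.6 might be the SD of the difference between the two changes. But the section says pre-posttest difference and ties 10 points to half an SD, and neither describes a difference of changes. Even on this reading, the SD is not justified for the contrast.
- **Power could be adequate.** This stands. Under reading A with equal SDs, a correlation between the changes of +0.25 gives 64% and +0.5 gives 81% at n = 36; with control-change SD 10 or 5, +0.25 gives 81% or 83%. By step 3, however, a positive value needs ρ13 below 2ρ - 1. At ρ = 0.5 that means scores 16 weeks apart correlating negatively. Because the baseline score is shared with opposite sign, a positive value is not the natural default. Reading B above ρ of about 0.8 also gives adequate power.
- **Some inputs are not the SAP's.** This also stands. Visit counts of 42, 42 and 39 are assumed; placing the early dropouts before the second visit moves mixed-model power by only about 1-2 points. Under reading A with equal score SDs, ρ = 0.9 implies a score SD of about 46 on a 0-100 scale, so the 56% end of that range is hard to credit.
- **The section never ties 80% to the contrast, and recruitment is over.** Both are true, and Table 3 already commits to a 95% CI for each change and for the contrast. That limits the harm. It does not alter the fact that the only stated power belongs to a quantity other than the primary one.

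**Conclusion.** The concern holds. The sample-size arithmetic is correct for one pre-post change but does not match the primary comparison, and the SAP does not show 80% power for that comparison.

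The size is conditional, not one figure. At ρ = 0.5, the only value where both uses of 20.6 agree, mixed-model power for a 10-point contrast is 42-49%. Less variation in the control period, or a higher correlation with 20.6 as a score SD, raises it to 80% or more. The SAP does not say which case applies, so it would be wrong to call the study underpowered as a fact. All figures rest on the assumptions listed with the calculation. This should be fixed; confidence in the mismatch is high.

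**What to change.** Change the Sample size section only:

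1. State that 36 patients and 80% power refer to one pre-post change in HAGOS pain, not to the primary between-period comparison.
2. State whether 20.6 is the SD of a score or of a change.
3. For the primary contrast, give power or expected 95% CI width over a stated range of control-period mean change, SDs of the two changes and their correlation. A short conditional range is enough, and since recruitment is complete, interval width is the more useful of the two.

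The cost is wording. Enrolment, estimand and model stay as they are; the SAP only gives up the implied 80% for its primary test.

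### Does the loose sentence on parametric or non-parametric methods leave the primary analysis unfixed?

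*SAP*

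**What the plan says.** The Statistical principles section opens with the check: "Descriptive data and fitted regression residuals from the mixed-effects linear regression model will be visually assessed for Gaussian distribution", by plots and by the Shapiro-Wilk test. The only stated consequence is that "Parametric and/or non-parametric statistical analyses will be used appropriately".

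Under Analysis methods the primary paragraph reads: "Under the assumption of normal distributed residuals, a mixed-effects linear regression model will be used" for the between-period change in HAGOS pain. The secondary paragraph sends the other five HAGOS subscales, EQ-5D-3L and pelvic tilt to the same model. The intention-to-treat claim rests on that model, which "will accommodate missing data in the analysis under the assumption" that data are missing at random. The Table 3 footnote repeats the link: "ITT=Intention To Treat (Mixed-effects linear regression model"). The Table 3 columns are mean, 95% confidence interval and P-value.

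The one explicit provision for non-Gaussian data is the Table 2 footnote on patient characteristics: "Gaussian distributed data will be presented as standard deviation (SD), otherwise as median and interquartile range (IQR").

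**The concern.** Three features make this look like a defect.

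- The sentence on parametric or non-parametric methods directly follows one that names the model residuals, and it speaks of analyses, not of descriptive tables.
- The primary paragraph can be read as conditional on normal residuals, with nothing said about what happens if they are not normal.
- No cut-off is tied to Shapiro-Wilk, plot and test are not ranked, and no non-parametric method is named.

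On that reading, two analysts could report different primary results from the same data. If one used a signed-rank test on each patient's between-period change, that test would need all three visits. Patients with a missing visit would drop out, and the test would not estimate the mean that Table 3 asks for. At stake would be the primary P-value, the quantity estimated and the set of patients analysed.

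**Working it through.** **1. The plan's own figure.** The Sample size section gives a 10-point difference, SD 20.6, alpha 0.05, power 80% and a minimum of 36. The standardised difference is 10/20.6 = 0.485. A two-sided paired t calculation first reaches 80% power at n = 36 (power 80.8%). The normal approximation, (20.6 × (1.960 + 0.842)/10)² = 33.3, gives 34. The figure reproduces, and it is a calculation on means, as is Table 3.

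**2. The text side by side.**

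| Place in SAP | Method named | Switch described? |
|---|---|---|
| Statistical principles | none specific | only in general terms |
| Primary analysis | mixed model | no |
| Secondary analysis | same mixed model | no |
| Table 3 footnote | mixed model is the ITT analysis | no |
| Table 2 footnote | SD, or median and IQR | yes, descriptive only |

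Every place that assigns an analysis to a Table 3 outcome assigns the mixed model. The phrase about normal residuals can be read as stating the model's assumption, not as one arm of a branch.

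**3. Patients at stake if a three-visit rank test were used.** Protocol deviations reports that "a total of 39 patients completed the training out of 42 included patients", so 42 − 39 = 3. The SAP does not say whether those three lack final HAGOS scores, so the loss is 0 to 3 of 42 (at most 3/42 = 7%). For pelvic tilt, "Three patients did not get the last EOS-scanning done after the end of the exercise period". Depending on overlap with the dropouts, the loss is 3 to 6 of 42 (7 to 14%).

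**4. Precision.** The between-period change is Y3 − 2·Y2 + Y1. Assume SD σ = 20.6 and equal within-patient correlation ρ = 0.6 (ρ is not in the SAP).

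- Complete patients only: variance = 6σ²(1 − ρ) = 6 × 424.36 × 0.4 = 1018.5, SD 31.9. The SE is 31.9/√39 = 5.11, or 31.9/√36 = 5.32.
- Keeping patients who lack only visit 3: each earlier visit predicts Y3 with slope ρ/(1 + ρ) = 0.375. The residual variance is 424.36 × (1 − 2 × 0.36/1.6) = 233.4. The part known for all 42 is 1.375·Y1 − 1.625·Y2, with variance 424.36 × 1.85 = 785.1.
- SE with 39 + 3: √(233.4/39 + 785.1/42) = 4.97. SE with 36 + 6: √(233.4/36 + 785.1/42) = 5.02.
- Cost of dropping the incomplete patients: 5.11/4.97 = 1.03 and 5.32/5.02 = 1.06.

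With first-order autoregressive correlation 0.7 the pairs are 3.88 against 3.79 (2%) and 4.03 against 3.85 (5%). For pelvic tilt only these ratios carry over.

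**5. Type I error.** Simulated with 39 complete patients, SD 20.6, ρ = 0.6 and 5,000 runs per setting.

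| Setting | Shapiro-Wilk switch | Smaller of two P-values |
|---|---|---|
| Normal | 5.0% | 5.8% |
| t, 5 df | 5.9% | 6.6% |
| Patient-varying variance | 4.7% | 5.6% |
| Ceiling | 5.3% | 6.3% |

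**6. Quantity estimated.** At a 10-point effect, the mean and the Hodges-Lehmann target are 10.0 and 9.9 if one third of patients gain 30 points, and 8.4 and 7.9 under a ceiling.

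**7. How often the choice would change the verdict.** At a 10-point effect the t-test and signed-rank test fall on opposite sides of 0.05 in 6 to 11% of trials. That counts trials where normality is not rejected and no switch is in question. It is also taken where 10/5.11 = 1.96, that is, near 50% power, where two tests disagree most. Counting only trials where Shapiro-Wilk rejects and the tests disagree (4,000 runs) gives 0.4% for normal data, 1.2% with a ceiling and 3.5% with t on 5 df. Strong patient-varying noise (log-SD 0.5, assumed) gives 11.6%.

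**The case for a change.** The strongest case for acting is that fixing the primary analysis is the SAP's core task, and this text does not say outright that the mixed model stands whatever the residuals show. The study is unblinded. Protocol deviations records that the pelvic-tilt outcome was changed after the radiographs were inspected, so some data had been seen. HAGOS is bounded at 0 and 100 and the EQ-5D index is capped at 1, so non-normal residuals are plausible. Nor can the sentence be confined to descriptive data with certainty, since the residuals are named just before it.

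There are also less favourable numbers. If the between-period difference is drawn from a skewed distribution with mean zero (gamma, shape 2, n = 39), the signed-rank test rejects in 11.6% of runs against 6.0% for the t-test, because it does not test the mean.

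The wording gap stands. The harm largely does not. The gamma result draws the contrast itself from an arbitrary skewed distribution; the ceiling setting, closer to a bounded score, gives 5.3% under the switch. The skewed case shows why a rank test would be a poor choice here, and the SAP does not prescribe one. The clash with Table 3 is also not general: a patient-level bootstrap of the mixed model is non-parametric, keeps all 42 patients and yields a mean with an interval. Finally, the general sentence has other work to do. Global Perceived Effect, the Oxford Hip Score and diary pain on a 0-10 scale have no method of their own, and limiting the sentence to descriptive tables would leave any inferential use of them without provision.

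**Conclusion.** The concern does not call for a change. The SAP leaves a detail to judgement, and the surrounding text tells the analyst how to fill it: fit the mixed model for every Table 3 outcome, treat the plots and Shapiro-Wilk as diagnostics, and use non-parametric summaries or tests where no model is assigned. Following the plan that way does not give a wrong result, and a fuller wording would keep the analysis already named.

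If an analyst did depart from the named model under a fixed switch, the simulated type I error is 4.7 to 5.9%, and 5.6 to 6.6% if the smaller P-value were reported. The standard error rises by 2 to 3% for HAGOS pain if three patients are lost, and by 5 to 6% for pelvic tilt if six are lost. These sizes rest on an assumed correlation (0.6 or 0.7) and assumed distributions. Strong skewness or strongly patient-varying noise would make them larger. The reading of the text depends on none of these assumptions.
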